#### **6.2.8 Plasma Exchange Histories**

PE history (including the one PE within 24 hours prior to randomisation) will be summarised for the ITT population. The number and percentage of subjects who had any pre-study PE history will be summarised by treatment group and overall. The total number of days for pre-study PE per subject will be summarised with descriptive

---

statistics: [n], arithmetic mean, standard deviation [SD], median, range (*i.e.* minimum and maximum values), and 95% confidence intervals for the mean.

PE history will be listed and will include date of TTP diagnosis, whether the subject has a history of PE (Yes or No), date of PE, number of days for PE, and plasma product. An asterisk will be placed indicating the PE which is given within 24 hours prior to randomisation.

## 6.3 Efficacy Analysis

### 6.3.1 Primary Efficacy Variable

#### *Primary endpoint*

Time-to-response, as defined in [Section 3](#), based on the following criteria:

- Recovery of platelets  $\geq 150,000/\mu\text{L}$
- This response must be confirmed at 48 hours after the initial reporting of platelet recovery equal to or above  $150,000/\mu\text{L}$  by a *de novo* measure of platelets  $\geq 150,000/\mu\text{L}$  and  $\text{LDH} \leq 2 \times \text{ULN}$  (*i.e.* “confirmed platelet response”)

Time-to-response will be measured in days, hours and minutes from date of first study drug administration. A Kaplan-Meier (KM) analysis with time-to-response as the end point and treatment group as the independent variable and stratified for absence/presence of one PE session prior to randomisation will be performed on the ITT and PP populations. An observation is censored if the observation does not meet the defined time interval of 30 days after first administration of study medication, due to any cause of loss-to follow-up (including death), or endpoint not being reached. The resulting survival estimates will be presented graphically. The median, 25th and 75th percentile time-to-event data will be presented in a table with 95% CIs (if they exist). ALX-0081 will be compared to placebo using a one-sided log-rank test in order to assess superiority at 2.5% significance level. The log-rank test is one-sided because a reduction in time-to-response by ALX-0081 is expected compared to placebo due to an inhibition of vWF by ALX-0081 (based on pre-clinical data).

---

### *Subgroup analyses*

In addition to the KM estimates, the corresponding Cox proportional hazard regression model with baseline disease characteristics (ADAMTS13 activity  $< 5\%$  versus  $\geq 5\%$ , vWF level (continuous), first episode versus recurrent disease (as described in [Section 6.2.4](#)), presence or absence of RICO suppression of  $< 20\%$  throughout treatment period, one PE prior to randomisation or not) will be used to estimate the hazard ratio (HR) and associated 95% CIs for the HR for ALX-0081 and placebo group. This will be represented by means of Forest plots.

The trial was not sized to test for the presence of treatment by subset interactions. Thus true treatment by subset interactions would likely be missed, unless they are substantial. Conversely, should any particular subset of subjects seem to benefit more or less from therapy than the total population, this would not be taken as evidence of a true treatment by subset interaction, given the likelihood that such an observation could be due to chance alone.

Underlying model assumptions will be investigated for the survival analysis using diagnostic statistics and graphical methods, and if necessary, an alternative analysis technique may be used. Any changes in methodology will be documented in the clinical study report (CSR, to be produced by [REDACTED]), including the rationale for use. The proportional hazards assumption will be assessed by graphical display of the log-log survival distribution function versus the log event time for each treatment group.

In order to accommodate tied time-to-event data, the EXACT option within SAS PROC PHREG shall be used. This method assumes that there is a true but unknown ordering for the tied event times, and that the ties are merely the results of imprecise measurements of time.

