### 6.1.2 Handling of Dropouts and Missing Data

The primary, secondary and longer term endpoint analyses will be based on available data. No imputations will be made for missing data unless otherwise specified.

If a subject had a PE prior to being randomised then there will be no replacement of missing baseline values by screening values. If a subject did not have a PE prior to being randomised then missing baseline values will be replaced by screening values. Missing data post-baseline will not be estimated or imputed for any of the parameters.

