### 6.1.4 Determination of Sample Size

The primary endpoint of time-to-response of blood markers (defined as time-to-response) is monitored in a survival setting. The time-to-response of blood markers comprises recovery of platelets  $\geq 150,000/\mu\text{L}$ . Accrual period was taken as 1.5 years. Actual accrual time is longer than 1.5 years; however there is no impact on the sample size. Zero to time to event period is set at 30 days. As median time-to-response for the control group we take 6 days (this information is calculated based upon Bandarenko *et al.*). For the treated group with ALX-0081 we assume a 44% risk reduction corresponding to a reduction in median time to event of 2.64 days, and ultimately resulting in a time-to-response of 3.36 days. The hazard ratio is defined in the SAS code as the ratio of control versus experimental (ALX-0081) treatment thus equaling to  $6/3.36=1.786$ . The sample size calculations are performed based on a log-rank test, aiming for a power of 80%, tested 1-sided at 2.5% significance level with 1:1 randomisation. Note that we assume that 15% of subjects would be lost-to-follow-up. The latter is justifiable because the active follow-up period (time of first study drug administration to time to event) only

---

equals 30 days. Based on the above described assumptions a sample size of 110 adult subjects is required. As subjects can be replaced, the ITT population may be larger than 110 subjects.

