### *Sensitivity analyses with regards to primary (and secondary) efficacy endpoints*

Sensitivity analyses comprise the following aspects:

- 1) For efficacy endpoints (EPs) (primary and secondary), analyses performed on per protocol (PP) populations. Details on major deviations are specified in [Appendix II](#).
- 2) Analysis of treatment effect adjusted for the following covariates:
  - a. ADAMTS13 activity at baseline: < 5% vs.  $\geq$  5%,
  - b. von Willebrand Factor (vWF) level (continuous),
  - c. first episode vs. recurrent disease (as described in [Section 6.2.4](#)),
  - d. Ristocetin Cofactor (RICO) suppression < 20% throughout treatment period: yes vs. no,
  - e. absence/presence of one PE session prior to randomisation.

A Cox proportional hazards model is fit to the data, and in addition to treatment, significant (5% significance level; SL) covariates are retained. This will be represented by means of Forest plots for the covariates found to be significant.

- 3) Analysis of non-confirmed and confirmed platelet response (instead of confirmed platelet response only) for the ITT population: see **Table 2**, with changes to
- 4) **Table 1** indicated in **bold green**.
- 5) Assessment of impact (potential bias) of use of rituximab during daily PE: log rank analysis of primary endpoint with subjects censored at time they start using rituximab for the ITT population. Use of rituximab will be determined by using the Concomitant Medications data (both PE related and not PE related) with ATC code “L01XC” (coded term “RITUXIMAB”).

**Table 2: Censoring/event scenarios (for ITT and PP analysis of non-confirmed and confirmed platelet response; changes to Table 1 indicated in bold green)**

Case	Description	Time at risk/ Time to recovery of platelets (days)	Responder	Censored (No = 0; Yes = 1)
1	No event in 30 days of continuous daily PE a	30	No	1
2	At day 30, confirmed recovery of platelets (per protocol)	30	Yes	0
3	At day x b (1 st measurement of platelet recovery), confirmed recovery of platelets, ideal case (per protocol)	x	Yes	0
4	No event occurred and subject is no longer in trial at day x b (including replaced subjects who are dosed)	x	No	1

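### SAP 6.3.1 plans no hazard ratio that matches the primary stratified comparison, and its subgroup Cox model adjusts for on-treatment RICO suppression and yields no subset hazard ratios

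*SAP*

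**What the plan says.** **Primary comparison (SAP 6.3.1, Primary endpoint, and the censoring and event plan).** The analysis is Kaplan-Meier by treatment, stratified by whether one PE was given before randomisation. It reports the median and quartiles with confidence intervals. The test is: "ALX-0081 will be compared to placebo using a one-sided log-rank test in order to assess superiority at 2.5% significance level". No HR is listed among these outputs.

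**Subgroup analyses (SAP 6.3.1).** The Cox model said to correspond to the Kaplan-Meier analysis carries five items described as baseline disease characteristics: ADAMTS13 activity below 5% or not, continuous vWF level, first or recurrent episode, RICO suppression below 20% over the treatment period, and prior PE. This model "will be used to estimate the hazard ratio (HR) and associated 95% CIs for the HR for ALX-0081 and placebo group", shown in Forest plots. The next paragraph says how to read the results "should any particular subset of subjects seem to benefit more or less from therapy than the total population".

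**Sensitivity analyses, item 2 (SAP 6.3.1).** The same five variables reappear under "Analysis of treatment effect adjusted for the following covariates". Treatment stays in the model, covariates significant at 5% are retained, and Forest plots show those covariates.

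**Sample size (SAP 6.1.4).** "As median time-to-response for the control group we take 6 days", and for ALX-0081 "we assume a 44% risk reduction corresponding to a reduction in median time to event of 2.64 days". The resulting HR is 6/3.36 = 1.786, with no covariates involved.

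**The concern.** Readers will look for an effect estimate beside the primary p-value. The estimates that the SAP offers differ from the primary comparison in three ways.

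- **A different quantity.** A Cox HR conditional on prognostic covariates is generally further from 1 than the HR from treatment alone, even under randomisation. It is not directly comparable with the log-rank result or with the design value of 1.786.
- **A post-randomisation covariate.** ALX-0081 is meant to work by inhibiting vWF, and RICO is the marker of that inhibition. Suppression over the treatment period is known only after dosing and is an effect of the drug. Conditioning on it removes the part of the benefit that passes through it. A significant log-rank result could then stand beside an HR near 1.
- **No subset effects.** The text discusses subsets that benefit more or less, but the model it writes gives one common treatment HR.

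The direction of the HR is also left open. SAP 6.1.4 labels 1.786 as control versus experimental, yet 6/3.36 is a ratio of medians. With exponential times it is the response hazard on ALX-0081 relative to placebo.

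**Working it through.** **1. Reproduce the design figure.** Inputs from SAP 6.1.4: medians 6 and 3.36 days, 15% loss, a 30-day window, and "aiming for a power of 80%, tested 1-sided at 2.5% significance level with 1:1 randomisation".

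- Schoenfeld events: 4 × (1.960 + 0.842)² / (ln 1.786)² = 31.4 / 0.336 = 93.4, so 94.
- Allowing for loss: 94 / 0.85 = 110.6, so 111.
- Event probability by day 30 (exponential): 1 − 2^(−30/6) = 0.969 on control and 1 − 2^(−30/3.36) = 0.998 on ALX-0081, mean 0.983. Then 94 / 0.983 gives 96, and 96 / 0.85 gives 113.

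The stated 110 is reproduced to within 3%. The HR behind it is a treatment-only HR.

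**2. Precision of that HR.** Expected events are 110 × 0.85 × 0.983 = 91.9. The standard error of the log HR is about 2/√91.9 = 0.209. At 1.786 the 95% CI is about 1.19 to 2.69.

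**3. Adjusted against treatment-only HR.** One simulated data set of 20,000 subjects was used per row, with exponential times, control median 6 days, a 30-day window and no dropout. The true conditional HR was 1.786. There were four baseline covariates: prior PE 30%, ADAMTS13 indicator 70%, standard normal vWF and recurrent episode 35%. Each had the log-HR shown. The prevalences and log-HRs are assumptions.

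| Log-HR per covariate | Adjusted HR | Treatment-only HR, stratified by prior PE | Ratio |
|---|---|---|---|
| 0 | 1.79 | 1.79 | 1.00 |
| 0.2 | 1.81 | 1.76 | 1.03 |
| 0.4 | 1.78 | 1.65 | 1.08 |
| 0.6 | 1.76 | 1.52 | 1.16 |
| 0.8 | 1.82 | 1.51 | 1.20 |

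The largest gap, ln 1.20 = 0.18, is below one standard error (0.209).

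**4. Adding RICO.** The same set-up was used, but with the whole effect assumed to run through suppression, reached by 85% on ALX-0081 and 2% on placebo. The log-HR of suppression was ln(1.786)/0.83, where 0.83 = 0.85 − 0.02. Across the five rows the RICO-adjusted treatment HR was 0.97, 1.00, 0.98, 1.00 and 0.99. The stratified treatment-only HR was 1.72, 1.65, 1.62, 1.50 and 1.47. A simulation at N = 110 under the same assumption about RICO gave about 1.04 against 1.75.

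The documents make a strong link between arm and suppression plausible. In the multiple-dose part of the subcutaneous Phase I study (Protocol Table 6), RICO fell below 20% in 6/6 + 6/6 = 12/12 subjects on ALX-0081 and in 0/2 + 0/2 = 0/4 on placebo. Protocol 10.5 justifies the one-sided test by expecting vWF inhibition in every treated subject. If suppression coincided exactly with arm, the two terms would be identical and the model could not separate them.

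**5. Analysis sets.** SAP Table 1, case 7, keeps a randomised but undosed subject in the primary analysis, censored at day 1. That subject has no treatment period in which RICO suppression could be defined, so the covariate model needs a rule that the SAP does not give.

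**6. What the subgroup paragraph can produce.** A single Cox model with treatment and five further terms returns one treatment HR and one prognostic HR per covariate. Subset HRs would need a treatment-by-factor term or separate fits within levels, and neither is written. Continuous vWF has no levels to plot.

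If subset HRs were fitted, their expected 95% CIs at 1.786 would be as follows (shares of events assumed):

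- 75% of events: 1.11 to 2.86
- 50%: 1.00 to 3.18
- 25%: 0.79 to 4.04
- 10%: 0.49 to 6.51

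A ratio of subset HRs would be detected with 80% power (two-sided 5%) only at about 3.2 for an even split of events, or 3.9 for 25:75.

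**The case against.** The strongest reply is that the paragraph is loosely drafted but its intention is clear. Its heading, the plural Forest plots and the guidance on reading subsets all suggest that subset HRs were meant. Covariate adjustment has its own place in sensitivity item 2, so a second copy would be redundant. Calling the model the one that corresponds to the Kaplan-Meier analysis hints at a link with the primary comparison. The SAP also warns against reading subset differences as real, and SAP 6.1.1 lets methods other than the primary analysis be replaced with a rationale in the CSR.

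Much of this is fair. A reader might infer that the SAP rules out interactions. It does not: it is silent. A reader might also infer that no treatment effect is shown in any subgroup. That goes too far, because SAP 6.3.2 shows several secondary endpoints by arm and ADAMTS13 category (descriptively), and SAP 6.3.6 is redacted.

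A third inference would be that many subjects drop out of the covariate model, since "No imputations will be made for missing data unless otherwise specified". The same section then replaces missing baseline values with screening values when there was no PE before randomisation, and Protocol 4.2 calls such a PE exceptional. The documents give no missingness rates, so no loss can be quantified.

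Three things still stand. Intention does not define a model, and Forest plots do not settle the matter, since item 2 uses them for covariates. Item 2 reduces to treatment alone only if no covariate is significant, which depends on the data, and even then it is not described as stratified. Neither the caution about subsets nor the clause on replacing methods removes RICO, and that clause would leave the model to be settled during the final analysis.

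**Conclusion.** The point holds for the primary endpoint. The visible text defines no HR from treatment alone, stratified by prior PE, in all ITT subjects. The two Cox models that give HRs include, or may select, an on-treatment marker of drug effect. The paragraph on subgroups does not specify how subset HRs would be obtained.

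The RICO term is the most serious part. If the effect ran wholly through suppression, the adjusted HR would be close to 1 while the treatment-only HR was about 1.5 to 1.7. That is an extreme case resting on the assumed 85% and 2%; partial mediation would give a smaller pull. Without RICO, the gap between adjusted and treatment-only HRs was 0 to 20% over the assumed covariate strengths, which is within one standard error at this trial size. These figures show direction and range and do not predict the trial's result.

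A reader might infer that the primary test or the sample size is undermined. Neither is: the log-rank test uses none of these covariates, and N = 110 is reproduced. What suffers is the effect estimate reported beside the test and the subgroup display. This should be corrected before database lock.

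**What to change.** In SAP 6.3.1:

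1. **Primary HR.** After the log-rank test, report the HR for ALX-0081 versus placebo, stating that a value above 1 favours ALX-0081, with its 95% CI. Take it from a Cox model with treatment only, stratified by prior PE, with exact handling of ties, all ITT subjects and the event and censoring rules of Table 1.
2. **Subgroups.** Replace the single model by one model per true baseline factor: ADAMTS13 activity (below 5% or not), first or recurrent episode, prior PE, and baseline vWF:Ag split at a cut fixed in advance, for example the pooled median. Each model has treatment, factor and their interaction. The Forest plot shows the HR, 95% CI, number of subjects and events per level, labelled exploratory.
3. **RICO and covariate adjustment.** Remove RICO suppression from the subgroup model and from sensitivity item 2. Keep covariate adjustment as sensitivity item 2 only.

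The cost is SAP wording and a few extra PROC PHREG calls, with no change to data collection, the primary test or the sample size. The downside is wide intervals in small subgroups, about 0.79 to 4.04 where a level holds 25% of the events. This fits the SAP's own statement that the trial was not sized for interactions.

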### *Censoring and event plan*

The primary endpoint in this trial is time to (initial) response. The event or response is defined as confirmed recovery of platelets above or equal to  $150,000/\mu\text{L}$ .

- Confirmed response means that 48 hours after the initial response, platelets remain above or equal to this cut-off (*de novo* measurement), and lactate dehydrogenase (LDH)  $\leq 2 \times$  upper limit of normal (ULN).
- ‘Time to’ is defined as time in days, hours and minutes between the event and the first administration of study drug. The initial time of reaching platelets above or equal to 150,000/ $\mu$ L is considered as the time of recovery of platelets, and must occur within 30 days after first administration of study drug. However, this initial recovery of platelets must be confirmed at 48 hours after initial reporting, implying that time of confirmation may be 48 hours later than 30 days after first administration.

Assessment of the primary endpoint is performed by using a one-sided log-rank test at 2.5% significance level. A Kaplan-Meier (KM) analysis with time-to-response as the endpoint and treatment group as the independent variable, and stratified for absence/presence of one PE session prior to randomisation, will be performed on the ITT population (all randomised subjects).

An observation is censored if the observation does not meet the defined time interval of 30 days after first administration of study drug medication, due to any cause of loss to follow-up (including death), or endpoint not being reached within the defined time interval. Only right censoring is applicable to this trial. In **Table 1**, different potential response (censoring/event) scenarios are presented.

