2.5.2 Potential Benefits

Although the introduction of PE and transfusion has significantly reduced the mortality rates from TTP over the last three decades, the condition still carries a significant risk of mortality and morbidity. The mortality rate of acute bouts in acute idiopathic TTP, in patients managed with the current therapies remains in the order of 10% to 30%.^{1,13,14} In the case of secondary TTP, PE and transfusion are recognised to be less effective and the mortality rate is considerably higher. In the cases when the disease is secondary to pregnancy, in which PE is regarded as reasonably effective the mortality rate of an acute bout of TTP is approximately 25%, rising to over 40% in cases with concurrent pre-eclampsia.¹⁵ However, in cases secondary to, for example, underlying malignancies or bone marrow transplant the mortality rate remains at 40% to 60% despite the use of such treatment regimens.^{14,16,17}

Potential effect of ALX-0081 on pathophysiology of TTP

ULvWF-mediated platelet aggregation is recognised as a key element in the pathogenesis of idiopathic TTP both in acute disease, in refractory and relapsing patients, and in the familial form of the disease. In secondary TTP, although the underlying etiologies are varied, ULvWF also appears to play a fundamental role in the underlying pathophysiological processes that have been proposed to underlie the condition. The inhibition of ULvWF-mediated platelet aggregation represents a rational approach to treatment that may prove to be of value in the management of all subtypes of TTP. Given the continuing significant level of mortality from TTP and the observed complications of PE and transfusion, there is a clear need for the development of such additional therapeutic approaches to supplement, or potentially reduce the need for, these methods of treatment. On the basis of the available information, ALX-0081 may offer such an additional option to further improve the management of TTP.

Potential benefit of ALX-0081 in TTP: efficacy

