10.5 Assessment of Primary Endpoint

The primary endpoint (i.e. time-to-response of blood markers comprising recovery of platelets $\geq 150,000/\mu\text{L}$) will be formally assessed by means of a survival analysis. An SAP will be prepared before closing the database and will comprise all methods and tests applied for analysis of the data.

Assessment of the primary endpoint is performed by using a one-sided log-rank test at 2.5% significance level. A Kaplan-Meier (KM) analysis with time-to-response as the endpoint and treatment group as the independent variable, and stratified for absence/presence of one PE session prior to randomisation, will be performed on the ITT and PP populations. An observation is censored if the observation does not meet the defined time interval of 30 days after first administration of study drug medication, due to any cause of loss-to follow-up (including death), or endpoint not being reached within the defined time interval.

The log-rank test is one-sided because inhibition by ALX-0081 of vWF is expected for all subjects. Indeed, as described in section 2.4.2, 100% of subjects receiving a SD s.c. injection of 8 mg already had inhibition of RICO up to a minimum of 18 hours.

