**Table 1: Censoring/event scenarios (for ITT and PP analysis of confirmed platelet response)**

Case	Description	Time at risk/ Time to recovery of platelets (days)	Responder	Censored (No = 0; Yes = 1)
1	No event in 30 days of continuous daily PE a	30	No	1
2	At day 30, confirmed recovery of platelets (per protocol)	30	Yes	0

Case	Description	Time at risk/ Time to recovery of platelets (days)	Responder	Censored (No = 0; Yes = 1)
3	At day x b (1 st measurement of platelet recovery), confirmed recovery of platelets, ideal case (per protocol)	x	Yes	0
4	No event occurred and subject is no longer in trial at day x b (including replaced subjects who are dosed)	x	No	1
5	At day x b (1 st measurement of platelet recovery), subject has recovery of platelets, however, missing data at 48 hours later, and no subsequent confirmation on platelet count during daily PE (no more daily platelet measurements) c	x	No	1
6	No recovery of platelets, however, daily PE stopped (daily PE considered surrogate for response d ). Except if PE stopped due to AE e (then idem case 4)	Time of last daily PE	No	1
7	Subject not dosed (after randomisation)	1	No	1

a PE = plasma exchange.

b At day x within 30 days assessment period.

c No subsequent confirmation during daily PE, since daily PE has been stopped by Investigator for clinical response which does not meet protocol definition of response.

d Certain subject's platelet counts 'hover' around 150,000/ $\mu$ L, and in clinical practice, PE is stopped.

e Start and stop dates of adverse events related to PE will need to be compared to PE stop dates in order to identify PE stopped due to AE.

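### Deaths before response are censored, so the Kaplan-Meier response curves and quartiles describe response as if nobody died; a cumulative-incidence display should stand beside them

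*SAP*

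**What the plan says.** Protocol 10.5 censors an observation that does not complete the 30-day window "due to any cause of loss-to follow-up (including death), or endpoint not being reached within the defined time interval". SAP section 3 (Time to Response) and SAP 6.3.1 carry the same rule, and the censoring and event plan repeats it: "due to any cause of loss to follow-up (including death".

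SAP Table 1 has no row for death. The row that fits is case 4, "No event occurred and subject is no longer in trial at day x": time at risk x, not a responder, censored. The subject leaves the risk set on day x.

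The KM curves are to be plotted, and "The median, 25th and 75th percentile time-to-event data will be presented in a table with 95% CIs (if they exist".

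The sensitivity analyses listed in SAP 6.3.1 are the per-protocol population, a covariate-adjusted Cox model, non-confirmed plus confirmed response (Table 2, where case 4 is unchanged), and censoring at the start of rituximab. None changes how a death is handled. Deaths are tabulated by arm and period in SAP 6.3.2, separately from time-to-response.

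**The concern.** Death before response is a competing event. When KM censors a subject, it assumes that the subject would have gone on to respond at the rate of those still at risk. That can be reasonable for someone who leaves the trial, but not for someone who has died. The curve then estimates a net quantity, response in the absence of death, while the plan presents it simply as time-to-response with quartiles.

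The direction is fixed. The proportion responded is too high and the percentile times are too short, in both arms.

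The issue is foreseeable here. The censoring rule itself names death, lower mortality is a secondary objective, and Protocol 2.5.2 says that mortality of an acute bout "in patients managed with the current therapies remains in the order of 10% to 30" percent.

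Table 2 adds a narrower gap. Its case 6 counts stopping daily PE without platelet recovery as a response, unless PE stopped because of an adverse event. Footnote e identifies that exception from adverse events related to PE. A subject who dies of TTP during daily PE also stops PE, and nothing in the table explicitly keeps that subject out of case 6.

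**Working it through.** **The plan's own figure.** SAP 6.1.4 states: "As median time-to-response for the control group we take 6 days". With 3.36 days on ALX-0081, the hazard ratio is 6/3.36 = 1.786. Schoenfeld events, one-sided 2.5%, 80% power: 4 × (1.960 + 0.842)² / (ln 1.786)² = 93.4. Dividing by 0.85 for the 15% loss gives 109.9, which reproduces 110. The sample size is not in question.

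**Inputs for the curve check.**
- Window: "Zero to time to event period is set at 30 days" (SAP 6.1.4).
- Response hazards, assumed exponential, λ = ln 2 / median: control 0.1155 per day, ALX-0081 0.2063 per day.
- Share d dying before response by day 30: not given in the documents, so assumed at 2%, 5% and 10%.

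**Formulas.**
- What KM shows: 1 − exp(−30λ). Control: 1 − 0.5⁵ = 96.9%. ALX-0081: 99.8%. Neither depends on d.
- Death hazard μ: solve μ/(λ+μ) × [1 − exp(−30(λ+μ))] = d.
- Cumulative incidence of response: F(t) = λ/(λ+μ) × [1 − exp(−(λ+μ)t)].
- Time by which a fraction p has responded: −ln[1 − p(λ+μ)/λ] / (λ+μ).

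**Worked line, control, d = 5%.** μ = 0.00625, λ+μ = 0.12178, λ/(λ+μ) = 0.9487. F(30) = 0.9487 × (1 − 0.0259) = 0.924. The 75th percentile is −ln(1 − 0.75/0.9487)/0.12178 = 12.8 days, against 12.0 by KM.

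| Arm | d | 1-KM, day 30 | Cumulative incidence, day 30 | Gap (points) | Median: KM → competing risk (days) | 75th percentile: KM → competing risk (days) |
|---|---|---|---|---|---|---|
| Control | 2% | 96.9% | 95.1% | 1.8 | 6.0 → 6.06 | 12.0 → 12.3 |
| Control | 5% | 96.9% | 92.4% | 4.5 | 6.0 → 6.15 | 12.0 → 12.8 |
| Control | 10% | 96.9% | 87.9% | 9.0 | 6.0 → 6.33 | 12.0 → 14.0 |
| ALX-0081 | 2% | 99.8% | 97.8% | 2.0 | 3.36 → 3.39 | 6.72 → 6.89 |
| ALX-0081 | 5% | 99.8% | 94.9% | 4.9 | 3.36 → 3.44 | 6.72 → 7.18 |
| ALX-0081 | 10% | 99.8% | 89.9% | 9.9 | 3.36 → 3.54 | 6.72 → 7.82 |

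With equal deaths in the arms, the contrast in medians hardly changes: 6.0 − 3.36 = 2.64 days by KM, against 6.15 − 3.44 = 2.71 days at 5%. The error is mainly in the level of each curve.

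**The test.** These are simulated trials with no effect on the response hazard and a nominal one-sided level of 2.5%.
- Deaths independent of prognosis: 2.4% to 2.6%, even when death rates differ by arm (for example 5% control against 15% ALX-0081).
- Deaths linked to prognosis but equal by arm (10% of subjects never respond, half of them die): about 2.7%.
- Deaths only among slow responders, 15% on ALX-0081 and 5% on placebo: 4.3% with 94 subjects, 4.7% with 110.
- More severe, deaths only among subjects who would never respond (20% of each arm; 75% of them die on ALX-0081 and 25% on control): 14.8%.

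Only the last two depart materially from the level. Both assume three times as many deaths on ALX-0081, concentrated in subjects with a poor outlook.

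**The case against.** Five points can be made for the plan.

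- **The primary test is sound.** A log-rank test with deaths censored is a standard test of the cause-specific response hazard, and the rule is stated openly in both documents. This stands. A reader might infer that the primary test is invalid. The documents do not support that, because the level fails only under the assumed prognosis-linked imbalance above. Such an imbalance should also show in the by-arm death table and in the DSMB's ongoing review of SAEs.
- **Some planned output already counts deaths as non-response.** SAP section 4 lists the percentage with confirmed platelet response, SAP 6.1.1 uses the whole population as denominator unless otherwise specified, and Table 1 case 4 codes the subject as a non-responder. Complete remission works the same way. So it would be wrong to say that nothing reveals the effect. These percentages have no time element, however, and do not correct the curves or quartiles.
- **The size may be small.** A reader might put the 10% to 30% mortality into the table and infer errors up to about 30 points. That range covers a whole acute bout, not death before platelet response within 30 days. Exclusion criteria 2, 9 and 12 also remove some of the sickest patients. It is at most an upper range.
- **The tabulated medians barely move.** True at 2% to 5% deaths. The 75th percentile moves more.
- **Holding deaths in the risk set to day 30 costs power.** Also true. Under the assumed effect, with 94 evaluable subjects, power falls from 0.76 to 0.51 at 5% deaths per arm and from 0.73 to about 0.36 at 10%. That analysis should not be a required check.

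SAP 6.3.5 and 6.3.6 are redacted, so the absence of a competing-risk estimate can be stated only for the readable text.

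**Conclusion.** The point holds for the displayed estimates. The KM curves and quartiles for time-to-response ignore death as a competing event, and no listed sensitivity analysis corrects them. The overstatement at day 30 is about 2 points at 2% deaths, 4-5 at 5% and 9-10 at 10%. Medians shift by a few tenths of a day at most, and the control 75th percentile by 0.3 to 2.0 days. These figures assume exponential response and death hazards, the plan's own medians, and a share of deaths that the documents do not state.

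The point does not extend to the log-rank test, the sample size or the choice of primary analysis. The possible loss of type I error control depends on deaths being both linked to prognosis and unequal by arm. Deaths before response reported by arm would show whether that needs discussion.

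**What to change.** Before database lock, leave the one-sided log-rank test and the KM analysis as specified, and amend SAP 6.3.1 as follows:

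- Add a cumulative-incidence curve of confirmed response by arm, with death before response as a competing event, and give its median and quartiles.
- Report the number of deaths before response by arm beside it.
- Add an explicit death row to Tables 1 and 2, coded as non-responder, so that a death during daily PE cannot be read as a response under Table 2 case 6.

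An analysis that keeps deaths in the risk set to day 30 may be added as a descriptive supplement, with its loss of power stated.

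The cost is SAP wording and one or two extra outputs. The displayed response estimates become somewhat less favourable, by an amount that depends on the number of deaths. No data collection, sample size or primary inference changes.
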